17.2.10 IV fluids

Within the group of patients admitted in the ICU the daily fluid balance (ml) will be compared between both groups using a multivariate normal model for longitudinal measurements, with the Aikake criterion to select the covariance matrix. The mean over d2-d5 will be compared, as well as the timepoint specific value. Study site will be added in the model. Note that the model will be fit on information from d1-d5, but restricted to the days the patient is in the ICU. For patients who die during ICU, the balance will be put on missing.

17.2.11 Quality of life (EQ-5D-5L)

The total scores will be compared between both groups using a multivariate normal model for longitudinal measurements, with the Aikake criterion to select the covariance matrix. the timepoint specific dosages. Study site will be added in the model. Note that the model will be fit on information from baseline – day 5 (or day of discharge if discharge before day 5), day 28 and month 3. For lost-to-FU and deceased patients, the score will be put on missing. Comparisons will refer to the three specific timepoints after baseline.

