8.3 Centre Effect

All statistical analyses of the outcomes of interest will be adjusted for study site. When applying the adjustment, the small site ULB Erasme (3 patients in the FAS) will be combined with UZ Brussels (Jette), as decided during the Blind review meeting (September 25, 2023).

9 Methods for Missing Data

In the statistical analyses of the longitudinally measured outcomes the presence of missing values is handled using a direct likelihood approach to fit the multivariate models. As such, the analysis is valid under the missing at random assumption (MAR).

Handling missing data for the SOFA score

In some settings, the following rules for single imputation will be used to handle missing SOFA scores or missing components for the calculation of the SOFA score.

- Patients who die within the time period of 5 days receive the worst outcome (highest SOFA score being equal to 24) starting at the day of death (even if a SOFA score is available at the day of death).
- SOFA scores are considered missing after the day of discharge
- If the patient's status does not require a lab analysis (due to good condition of the patient), missing data occur as per protocol. In this case the best possible score will be used for the SOFA score calculation (i.e. 0 points for bilirubin, blood platelets and creatinin) in the daily follow-up.
- If however a lab analysis was not ordered but was required as per protocol, the SOFA score of that day will be considered as missing.
- If a lab analysis was required, but one of the three lab values needed in the SOFA score was missing, the previous lab value was used for the calculation of the SOFA score. This was deemed appropriate, since it can be assumed that the specific lab parameter was not ordered that day because the function was considered stable. In rare cases where this happened at d1, the value of d2 will be used for the calculation of the SOFA score.

Frequency tables will be reported for the various settings where above imputation rules were applied.

For the analysis of the maximal SOFA score a multiple imputation approach will be used (cfr infra for details of the imputation model).

10 Data Transformations

An inverse hyperbolic sign transformation will be applied in the analysis of the (maximal) SOFA to obtain a more symmetric distribution of the model residuals. Analyses on untransformed scores will be reported as sensitivity analyses.

11 Multicenter Study

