17.2.12 Return to work

For patients who were at work before inclusion in the study, the time until return to work will be compared. Patients lost-to-FU and patients not returned to work (at three months) are censored. Deceased patients are treated as a competing risk. The comparison will be based on a stratified Gray's test.

18 Adverse Events

The number of events and the number of patients experiencing adverse events will be summarized by treatment group.

Separate summaries will be presented for:

- Serious adverse events
- Serious or severe adverse events
- Treatment-related adverse events
- Treatment-related serious adverse events.

Summaries of adverse events will be presented only for the FAS.

19 Other Data

All other data will be summarized by treatment group and, if applicable, by day.

20 References

- Liang K-Y, Zeger SL. Indian Statistical Institute Longitudinal Data Analysis of Continuous and Discrete Responses for Pre-Post Designs. *Indian J Stat Ser B Ser B Biostat.* 2000;62(1):134-148. doi:10.2307/25053123
- SAS software, version 9.4 of the SAS System for Windows. Copyright © 2002 SAS Institute Inc. SAS and all other SAS Institute Inc. product or service names are registered trademarks or trademarks of SAS Institute Inc., Cary, NC, USA
- Stroup, W. Mixed model procedures to assess power, precision, and sample size in the design of experiments. *Proc. Biopharmaceutical Section. Am. Stat. Assoc., Baltimore, MD 15-24 (1999).*

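### EQ-5D-5L scores after death are treated like scores missing at random, so this comparison describes a population in which nobody died and barely registers a survival difference

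*SAP*

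**What the plan says.** SAP section 17.2.11 (Quality of life) states: "The total scores will be compared between both groups using a multivariate normal model for longitudinal measurements". It fits baseline, day 5 (or discharge if earlier), day 28 and month 3, and adds: "Comparisons will refer to the three specific timepoints after baseline". For absent scores it has one rule: "For lost-to-FU and deceased patients, the score will be put on missing".

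Section 9 (Methods for Missing Data) supplies the method: "In the statistical analyses of the longitudinally measured outcomes the presence of missing values is handled using a direct likelihood approach". It concludes that the analysis is then valid under missing at random (MAR).

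Neither section names a survivor-only target, a value at death, a composite or a sensitivity analysis for EQ-5D-5L. Section 17.2.11 also does not say which EQ-5D-5L score the total score is.

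The next section, 17.2.12 (Return to work), runs over the same three months. It censors patients lost to follow-up but handles death differently: "Deceased patients are treated as a competing risk".

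**The concern.** Direct likelihood under MAR treats a missing value as one that exists but was not seen, and predicts it from the patient's observed scores. That is reasonable for a living patient who misses a visit. A patient who has died has no score to predict. The fitted day-28 and month-3 means therefore refer to a hypothetical population in which everyone lived to be assessed.

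The interpretation of one endpoint is at stake. A reader of the month-3 result may take it as quality of life among survivors, or as the overall effect with death counted, and it is neither. If one arm keeps more patients alive, the EQ-5D-5L comparison will hardly show it. Month 3 is the most exposed time point, because deaths have accrued longest there and the SAP lists no mortality comparison at that time.

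**Working it through.** **Inputs.** The SAP gives no EQ-5D-5L mean or SD and no mortality rate, so there is no figure of the plan to reproduce. From the SAP come the missing-data rule and model (17.2.11, section 9), 150 patients per arm (section 6) and two-sided alpha of 0.05 (section 17). All else below is assumed, including an index on which death is 0.

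**Step 1: algebra.** For one arm and time point, let m be the proportion dead, S the mean score of the living, and P the mean score that the fitted model implies for the dead.

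- Planned mean: (1 − m)S + mP
- Mean with death scored 0: (1 − m)S

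If S and P are equal in the two arms, the treatment-minus-control differences are:

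- Planned: (m_C − m_T)(S − P)
- Death scored 0: (m_C − m_T)S

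The planned analysis thus weights a survival difference by the gap between survivors and the model's prediction for the dead, which is small. With S = 0.70:

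- 20% vs 15% mortality, death scored 0: 0.85 × 0.70 − 0.80 × 0.70 = 0.595 − 0.560 = 0.035
- 20% vs 10% mortality, death scored 0: 0.90 × 0.70 − 0.80 × 0.70 = 0.630 − 0.560 = 0.070
- 20% vs 15%, planned, P = 0.70: 0.05 × 0 = 0
- 20% vs 15%, planned, P = 0.56 (the lowest value in Step 2): 0.05 × 0.14 = 0.007
- Equal mortality: 0 under both

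**Step 2: fitting the planned type of model.** An unstructured multivariate normal model was fitted by maximum likelihood to simulated data with 60,000 patients per arm. Assumed latent means were 0.55, 0.60, 0.68 and 0.72 at baseline, day 5, day 28 and month 3, with SD 0.25 and correlation 0.5. Latent quality of life was the same in both arms, so only survival differed. Death was either unrelated to the baseline score or more likely when it was low.

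| Day-28 mortality (month 3) | Death related to baseline score | Planned difference, day 28 / month 3 | Death scored 0, day 28 / month 3 | Score implied for dead controls, day 28 / month 3 |
|---|---|---|---|---|
| 12% vs 6% (15% vs 7.5%) | no | 0.000 / 0.001 | 0.041 / 0.055 | 0.682 / 0.720 |
| 12% vs 6% (15% vs 7.5%) | yes | 0.001 / 0.000 | 0.036 / 0.047 | 0.560 / 0.610 |
| 20% vs 15% (25% vs 18%) | no | −0.003 / −0.001 | 0.031 / 0.049 | 0.679 / 0.720 |
| 20% vs 15% (25% vs 18%) | yes | 0.001 / 0.001 | 0.031 / 0.048 | 0.576 / 0.627 |
| 30% vs 20% (35% vs 24%) | no | −0.002 / −0.001 | 0.067 / 0.079 | 0.680 / 0.720 |
| 30% vs 20% (35% vs 24%) | yes | −0.002 / −0.004 | 0.062 / 0.073 | 0.598 / 0.648 |
| 20% vs 20% (25% vs 25%) | no | 0.001 / −0.001 | 0.001 / −0.001 | 0.680 / 0.721 |
| 20% vs 20% (25% vs 25%) | yes | 0.002 / 0.002 | 0.001 / 0.001 | 0.575 / 0.627 |

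The planned differences all lie within 0.004 of zero. With unequal mortality, scoring death as 0 gives 0.031 to 0.067 at day 28 and 0.047 to 0.079 at month 3.

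**Step 3: does the separate mortality test cover the gap?** Section 17.2.5 compares mortality at 28 days only. An ordinary two-proportion test (ignoring site) at 150 per arm has power of about 44% for 12% vs 6%, 21% for 20% vs 15%, and 52% for 30% vs 20%. It can miss differences of this size, and it says nothing about deaths between day 28 and month 3.

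**The case against.** The strongest reply is that the rule is explicit and reproducible, that a hypothetical target is a legitimate choice, and that mortality has its own endpoint. Much of this stands, and it rules out three stronger readings.

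- **A reader might infer that the plan hides a survival benefit of the trial.** It does not. Section 17.2.5 tests 28-day mortality with confidence intervals and an odds ratio, and section 15 tabulates in-hospital deaths to day 5 by arm. The point is limited to the EQ-5D-5L comparison.
- **A reader might infer that the SAP contradicts itself**, since SOFA is set to 24 from the day of death and death is a competing risk for length of stay. But vasopressors, renal replacement, ventilation, steroid dose and fluid balance (17.2.6 to 17.2.10) also set death to missing. Those outcomes cover days 1 to 5, whereas EQ-5D-5L runs to month 3. The contrast with return to work therefore weakens the case for the rule without making it a contradiction.
- **A reader might infer that the arm with better survival would look worse on EQ-5D-5L.** In the simulation this happened only for raw survivor means, by 0.005 to 0.014 when death depended on baseline score. The planned model showed nothing beyond 0.004.

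It is also fair that every EQ-5D-5L and mortality figure above is assumed, and that the endpoint is one of several exploratory secondary outcomes without multiplicity control (section 13). A hypothetical target can be defended when it is named and justified. Here it arises by default from the missing-data rule.

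**Conclusion.** The point holds for the EQ-5D-5L comparison. Sections 17.2.11 and 9 together yield means for a population without deaths, and nothing else in the SAP repairs this for EQ-5D-5L. The planned contrast is nearly blind to survival differences: about 0 where a death-inclusive score would differ by roughly 0.03 to 0.08 under the assumed scenarios, and the same as other approaches when mortality is equal. These sizes depend on the assumed mortality, the assumed scores and the value 0 for death. The mechanism does not depend on them. The primary analysis and the sample size are unaffected. This is an inexpensive improvement to a secondary endpoint.

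**What to change.** Revise section 17.2.11 as follows.

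1. State that the total score is the EQ-5D-5L index. If another score is meant, fix its value at death to suit its scale and direction.
2. Separate death from loss to follow-up, and keep MAR only for living patients with a missing score. The multiple imputation already planned in 17.2.4 is one way to fill those scores using living patients only.
3. Add a prespecified analysis with death scored 0 from the date of death at all three post-baseline time points: day 5 or discharge, day 28 and month 3. Use a method that tolerates the spike at 0, such as robust standard errors or a rank-based comparison with death as the worst rank.
4. Report a survivors-only summary beside it, labelled as conditional on survival, with the number of deaths per arm at each time point.

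The cost is a few sentences and one additional analysis of data already collected. The downside is that the death-inclusive result partly reflects mortality and the survivors-only summary is not a randomised comparison, which is why both should be shown.

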17.2.12 Return to work

For patients who were at work before inclusion in the study, the time until return to work will be compared. Patients lost-to-FU and patients not returned to work (at three months) are censored. Deceased patients are treated as a competing risk. The comparison will be based on a stratified Gray's test.

18 Adverse Events

The number of events and the number of patients experiencing adverse events will be summarized by treatment group.

Separate summaries will be presented for:

- Serious adverse events
- Serious or severe adverse events
- Treatment-related adverse events
- Treatment-related serious adverse events.

Summaries of adverse events will be presented only for the FAS.

19 Other Data

All other data will be summarized by treatment group and, if applicable, by day.

20 References

- Liang K-Y, Zeger SL. Indian Statistical Institute Longitudinal Data Analysis of Continuous and Discrete Responses for Pre-Post Designs. *Indian J Stat Ser B Ser B Biostat.* 2000;62(1):134-148. doi:10.2307/25053123
- SAS software, version 9.4 of the SAS System for Windows. Copyright © 2002 SAS Institute Inc. SAS and all other SAS Institute Inc. product or service names are registered trademarks or trademarks of SAS Institute Inc., Cary, NC, USA
- Stroup, W. Mixed model procedures to assess power, precision, and sample size in the design of experiments. *Proc. Biopharmaceutical Section. Am. Stat. Assoc., Baltimore, MD 15-24 (1999).*
- Van Buuren, S. (2007), “Multiple Imputation of Discrete and Continuous Data by Fully Conditional Specification,” *Statistical Methods in Medical Research,* 16, 219–242.

Addendum 1: Calculation of SOFA score

GCSc=categorised Glasgow Coma Score (GCS).
 15: 15
 16: 13-14
 17: 10-12
 18: 6-9
 19: <6

Platelets= categorised platelets ($\times 10^3/\mu\text{L}$)
 1: ≤ 150
 2: 100-149
 3: 50-99
 4: 20-49
 5: <20

BilirubinC=categorised bilirubin in mg/dL (or $\mu\text{mol/L}$)
 1: <1.2 (<20)
 2: 1.2-1.9 (20-32)
 3: 2.0-5.9 (33-101)
 4: 6.0-11.9 (102-204)
 5: ≥ 12.0 (>204)

CreatinineC=categorised creatinin in mg/dL (or $\mu\text{mol/L}$)
 1: <1.2 (<110)
 2: 1.2-1.9 (110-170)
 3: 2.0-3.4 (171-299)
 4: 3.5-4.9 (300-400) or UOP<500mL/day
 5: ≥ 5 (>440) or UOP<200mL/day

VasoDose=categorised administered vasoactive agents (mcg/kg/min)
 1: dopamine ≤ 5 or dobutamine (any dose)
 2: dopamine > 5 epinephrine ≤ 0.1 or norepinephrine ≤ 0.1
 3: dopamine > 15 epinephrine > 0.1 or norepinephrine > 0.1

MAPc=categorised mean arterial pressure (mmHg)
 1: ≥ 70
 2: <70

PaO2FiO2c=categorised PaO₂/FiO₂ (mmHg)
 1: ≥ 400
 2: 300-399
 3: 200-299
 4: ≤ 199 and NOT mechanically ventilated
 5: 100-199 and mechanically ventilated
 6: <100 and mechanically ventilated

O2FiO2c O2Sat/FiO2 (mmHg)
 1: > 400
 2: ≤ 400
 3: ≤ 315
 4: ≤ 235
 5: ≤ 150

lab_anal_day: was a lab analysis ordered?
 0: No
 1: Yes

nolab_analreas_day: Why was a lab analysis not ordered?
 1: not needed due to the good condition of the patient
 2: lab analysis was forgotten

Fudate: follow-up date
 Deathdate: day of death

```

SOFA=0;
if GCSc=15 then SOFA=SOFA+0;
if GCSc=16 then SOFA=SOFA+1;
if GCSc=17 then SOFA=SOFA+2;
if GCSc=18 then SOFA=SOFA+3;
if GCSc=19 then SOFA=SOFA+4;
if PlateletsC=1 then SOFA=SOFA+0;
if PlateletsC=2 then SOFA=SOFA+1;
if PlateletsC=3 then SOFA=SOFA+2;
if PlateletsC=4 then SOFA=SOFA+3;
if PlateletsC=5 then SOFA=SOFA+4;
if BilirubinC=1 then SOFA=SOFA+0;
if BilirubinC=2 then SOFA=SOFA+1;
if BilirubinC=3 then SOFA=SOFA+2;
if BilirubinC=4 then SOFA=SOFA+3;
if BilirubinC=5 then SOFA=SOFA+4;
if CreatinineC=1 then SOFA=SOFA+0;
if CreatinineC=2 then SOFA=SOFA+1;
if CreatinineC=3 then SOFA=SOFA+2;
if CreatinineC=4 then SOFA=SOFA+3;
if CreatinineC=5 then SOFA=SOFA+4;
if VasoDose=. then do;
  if MAPc=1 then SOFA=SOFA+0;
  if MAPc=2 then SOFA=SOFA+1;
  end;
if VasoDose^=. then do;
  if VasoDose=1 then SOFA=SOFA+2;
  if VasoDose=2 then SOFA=SOFA+3;
  if VasoDose=3 then SOFA=SOFA+4;
  end;

if PaO2FiO2c=1 then SOFA=SOFA+0;
if PaO2FiO2c=2 then SOFA=SOFA+1;
if PaO2FiO2c=3 then SOFA=SOFA+2;
if PaO2FiO2c=4 then SOFA=SOFA+2;
if PaO2FiO2c=5 then SOFA=SOFA+3;
if PaO2FiO2c=6 then SOFA=SOFA+4;

if O2FiO2c=1 then SOFA=SOFA+0;
if O2FiO2c=2 then SOFA=SOFA+1;
if O2FiO2c=3 then SOFA=SOFA+2;
if O2FiO2c=4 then SOFA=SOFA+3;
if O2FiO2c=5 then SOFA=SOFA+4;

*deceased patients receive maximal score from the day of death on;
if Fudate>=Deathdate>.z then SOFA=24;

*when lab analysis is forgotten, SOFA is put on missing;
if nolab_analreas_day=2 then SOFA=.;

*when info is missing if a lab analysis was performed, SOFA is put on missing;
if lab_anal_day<=.z then SOFA=.;

*if no lab analysis is performed and there is no information on the reason of a
missing lab analysis, SOFA is put on missing;
if lab_anal_day=0 and nolab_analreas_day not in (1,2) then SOFA=.;
```

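### As printed, the SOFA program adds both oxygen ratios when both are recorded (total up to 28, not 24) and scores 0 for a blank non-laboratory item

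*SAP*

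**What the plan says.** Addendum 1 sets SOFA to 0 and adds points item by item.

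- **Respiratory item.** The PaO2/FiO2 block ends with "if PaO2FiO2c=6 then SOFA=SOFA+4". The O2Sat/FiO2 block follows directly and ends with "if O2FiO2c=5 then SOFA=SOFA+4". Neither tests whether the other variable is filled.
- **Cardiovascular item.** Here two fields also compete for one item, and the program does set a precedence. MAP is used only under "if VasoDose=. then do"; otherwise the vasoactive category counts.
- **Setting the score to missing.** Three statements do this: "if nolab_analreas_day=2 then SOFA", "if lab_anal_day<=.z then SOFA" and "if lab_anal_day=0 and nolab_analreas_day not in (1,2) then SOFA". All three look only at whether a laboratory analysis was done and why not.

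Section 9 describes the death score as the "highest SOFA score being equal to 24". Its rules for missing components concern bilirubin, platelets and creatinine. Where the patient's good condition made a laboratory analysis unnecessary, it says: "In this case the best possible score will be used for the SOFA score calculation". It gives no rule for a missing GCS, MAP, vasoactive or oxygen entry. Section 16 lists PaO2/FiO2 as the only respiratory component of the d1 score.

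**The concern.** The addendum is the SAP's only scoring specification, so it is taken here to define every SOFA value: the d1 value in the cLDA response, the d2-d5 scores behind the primary endpoint, the daily comparisons, the maximal score, and the baseline subgroups (<6 versus ≥6). Read literally, it lets a score depend on which boxes were filled as well as on organ function.

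The two faults pull in opposite directions. Two recorded ratios count the lungs twice and can place a living patient above the value reserved for death. A blank bedside item is treated as normal organ function, a best-case imputation that Section 9 does not list. The Section 9 frequency tables cover the listed imputation rules, so they would not show it.

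**Working it through.** **Inputs, all from Addendum 1.** `PaO2FiO2c` 1 to 6 earns 0, 1, 2, 2, 3, 4 points. `O2FiO2c` 1 to 5 earns 0, 1, 2, 3, 4. GCS, platelets, bilirubin, creatinine and the cardiovascular item earn at most 4 each. A blank matches no IF statement and adds 0.

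**The plan's own figure.** With all items at worst and one oxygen ratio filled, the total is 5 × 4 + 4 = 24. Either ratio alone reproduces the maximum in Section 9.

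**Test records run through the printed statements:**

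| Record | Printed program gives |
|---|---|
| All worst, both ratios filled | 5 × 4 + 4 + 4 = 28 |
| Both ratios worst, all else normal | 4 + 4 = 8 |
| `PaO2FiO2c`=5 and `O2FiO2c`=4, all else normal | 3 + 3 = 6 |
| All worst (24), GCS blank | 20 |
| All worst (24), vasoactive category and MAP blank | 20 |
| All worst (24), both ratios blank | 20 |
| All items blank, laboratory analysis done | 0 |
| All items blank, no analysis because of good condition | 0 |
| All items blank, laboratory question unanswered | missing |

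A blank vasoactive category alone is not a fault: it falls through to MAP as intended. A blank laboratory value on a day with an analysis also scores 0 in these lines, but Section 9 has a carry-forward rule for that, so it is not counted here.

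**Baseline subgroup.** When both ratios earn equal points, 1, 2, 3 and 4 become 2, 4, 6 and 8. The last two meet the ≥6 cut on the respiratory item alone, which one ratio (maximum 4) cannot do. A blank item on d1 can move a patient the other way.

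**Primary scale.** The primary analysis transforms the scores; the transformation is read here as the inverse hyperbolic sine.

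- A 2 recorded as 4: asinh(4) − asinh(2) = 2.09 − 1.44 = 0.65, a ratio of about 1.9.
- A 4 recorded as 0: 2.09 − 0 = 2.09.
- A 24 recorded as 28: about ln(28/24) = 0.15.

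On that scale, errors at low scores weigh most.

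**Illustration of double counting under assumed frequencies.** The SAP gives no frequency. Assume that a share p = 5% to 20% of patient-days have both ratios, with m = 1 to 3 extra points that are independent of the underlying score. On the untransformed scale:

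- Rise in mean SOFA in each arm = p × m: 0.05 × 1 = 0.05 to 0.20 × 3 = 0.60.
- SD = √(3.5² + p(1 − p)m²): √(12.25 + 0.0475) = 3.51 to √(12.25 + 1.44) = 3.70, where 3.5 is the planning SD in Section 6.

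At p = 0 both effects vanish.

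**The case against.** The strongest reply is that the harm depends on data capture that the SAP does not show. If the case report form accepts one ratio and forces every item, nothing goes wrong, and the single respiratory component in Section 16 fits O2Sat/FiO2 being a substitute. The addendum is also not the whole data flow: Section 9 requires carry-forward of laboratory values and missing scores after discharge, and neither is in the printed lines, so other steps must exist. The SAP was finalised after blind review meetings, and the gaps it discusses are laboratory gaps; nothing shows that bedside items were ever blank. All of this stands as a limit on how often the fault occurs. It does not cure the specification. No sentence makes the ratios exclusive, and the authors coded both a precedence for MAP and checks for blank laboratory answers, so they did not rely on clean capture elsewhere.

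A reader might also infer three stronger claims, which the document does not support.

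- *The treatment comparison is biased.* Nothing suggests that fill rates differ between arms. The comparison is randomised against placebo, so without a treatment effect the expected difference in fill rates is zero. If double filling follows severity, it mainly reweights a real difference.
- *Power is lost.* Even the assumed worst SD of 3.70 lies below 3.5 × √(300/252) = 3.82, the SD at which 300 patients match the planned precision of 252. That margin was meant for death imputation, so this limits the worry without removing it.
- *A day can lose 12 points, or an empty day scores 0.* Three blank items whose true scores are all 4 would be needed (3 × 4 = 12); that is a coding ceiling. A day whose laboratory question is also blank is set to missing.

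**Conclusion.** The point holds for the program as printed. With both ratios filled, the respiratory item can be doubled, up to 8, and the total can reach 28 against a stated maximum of 24. On days with a valid laboratory answer, each blank GCS, cardiovascular or respiratory item lowers the score by between 0 and 4 points without a stated rule. Because this code defines the primary endpoint, it is a wrong scoring rule for such records and not merely missing detail.

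The number of affected patient-days is unknown and may be zero. At equal rates in both arms the result is mainly noise and, for double counting, extra weight on the respiratory organ. One double-counted day can still set a patient's maximal SOFA, and on d1 either fault can change the subgroup. The conclusion assumes that the printed lines are applied as they stand and that no unseen step removes one ratio or fills the blanks. It is worth correcting because the primary endpoint should be reproducible from its own specification.

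**What to change.** 1. Make the O2Sat/FiO2 block conditional on PaO2/FiO2 being blank, in line with the component listed in Section 16. Alternatively, state in Section 9 that data capture allows only one ratio per day.
2. Replace the silent zero with an explicit rule for a blank GCS, a blank cardiovascular item (neither vasoactive category nor MAP) and two blank oxygen ratios: either set the score to missing or use a stated imputation.
3. Add to the Section 9 frequency tables, by arm and day, the number of records with both ratios filled and with each non-laboratory item blank. If the counts are zero, the point is closed.
4. Add a check that every score lies in 0-24.

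The cost is a few lines of SAS and one or two sentences in Section 9. If missing is chosen, a few more patient-days may rely on the missing-at-random assumption of the planned model, and the other valid items of those days are lost; a stated imputation avoids that loss at the price of a further assumption.

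### As printed, the Addendum 1 SOFA program can turn a deceased patient's 24 into a missing value, against the death rule in sections 6 and 9

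*SAP*

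**What the plan says.** SAP section 9 (Methods for Missing Data) says that patients who die within the five-day period "receive the worst outcome (highest SOFA score being equal to 24) starting at the day of death", and adds that this applies "even if a SOFA score is available at the day of death". Section 6 states the same rule without the number 24 and without that added clause. Neither section makes the rule depend on laboratory data.

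The SOFA program in Addendum 1 carries the matching comment, "deceased patients receive maximal score from the day of death on", followed by the statement "if Fudate>=Deathdate>.z then SOFA=24". Three statements come after it, each setting SOFA to missing:

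- "if nolab_analreas_day=2 then SOFA" (lab forgotten);
- "if lab_anal_day<=.z then SOFA" (lab-ordered field empty);
- "if lab_anal_day=0 and nolab_analreas_day not in (1,2) then SOFA" (no lab, and no valid reason recorded).

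The lab-ordered field has codes for no and yes only. The second field is defined as "nolab_analreas_day: Why was a lab analysis not ordered", with code 1 for a patient well enough not to need one and code 2 for a forgotten lab. Neither field has a code for a deceased patient.

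**The concern.** The statements run in printed order, so the last assignment that applies wins. A deceased patient first receives 24 and can then be set to missing by a rule that looks only at laboratory fields. That contradicts the written death rule and the program's own comment.

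Three sets of results depend on these scores:

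- **Primary endpoint (17.1) and day-specific SOFA (17.2.3).** A lost 24 enters the cLDA as missing at random, so the model fills the gap implicitly from the patient's other scores instead of applying the worst score.
- **Maximal SOFA (17.2.4).** A patient with no 24 left has a lower maximum. If imputation is used, which the SAP limits to scores missing for administrative reasons, the models regress each day on the other days within arm. Losing the 24s then also changes other patients' imputed scores.
- **Design.** Section 6 raised the sample from 126 to 150 per group because of the extra variability expected from these maximal scores.

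**Working it through.** **1. Trace of the program.** Take a patient whose follow-up date is on or after the death date, and run the four closing statements in printed order over all combinations of `lab_anal_day` and `nolab_analreas_day`.

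| Lab ordered | Reason | As printed | Death statement last |
|---|---|---|---|
| empty | empty | missing | 24 |
| empty | 1 | missing | 24 |
| empty | 2 | missing | 24 |
| 0 | empty | missing | 24 |
| 0 | 1 | 24 | 24 |
| 0 | 2 | missing | 24 |
| 1 | empty | 24 | 24 |
| 1 | 1 | 24 | 24 |
| 1 | 2 | missing | 24 |

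The 24 is kept in 3 of 9 combinations. A reason makes sense only when no lab was ordered, which leaves five coherent combinations: (1, empty), (0, 1), (empty, empty), (0, 2) and (0, empty). The 24 is kept in the first two and lost in the other three. These counts describe the logic and say nothing about frequency. An empty lab field always loses the 24. With the death statement last, all nine give 24, and living patients' results do not change.

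**2. One patient.** Assume a score of 8 before death, lab fields filled through the day of death and empty afterwards. Death on d3 gives 8, 24, missing, missing over d2-d5 (observed mean (8+24)/2 = 16.0) instead of 8, 24, 24, 24 (mean 80/4 = 20.0).

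**3. Scale in the trial (illustration).** Mortality, its timing and survivor scores are assumptions; the SAP gives none of them. Assume 8% versus 4% dead by d5, deaths spread evenly over d2-d5, and no treatment effect in survivors.

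- Deaths at 150 per group: 12 + 6 = 18.
- Dead days per death: (4+3+2+1)/4 = 2.5, so 18 × 2.5 = 45 scores of 24.
- Share of planned d2-d5 scores: 45/(300 × 4) = 3.75%.
- On the day of death 18; after it 45 − 18 = 27.

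**4. Effect on the primary contrast (same scenario).** Simulation with 3 × 120,000 patients per arm, SD 3.5 and correlation 0.5 (section 6) before rounding, survivor means 6, 5.5, 5, 4.5, 4 over d1-d5, death log-odds rising 0.7 per baseline SD, and a cLDA with unstructured covariance. The Monte Carlo SD of the asinh contrast is at most 0.0007. The contrast is the lower-mortality arm minus the higher-mortality arm. In the last three columns every score after the day of death is lost, and the stated share of death-day 24s is kept.

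| Mortality | Written rule | 100% kept | 50% kept | 0% kept |
|---|---|---|---|---|
| 8% vs 4% | −0.0428 | −0.0237 | −0.0115 | 0.0011 |
| 10% vs 5% | −0.0535 | −0.0301 | −0.0147 | 0.0013 |
| 6% vs 4% | −0.0214 | −0.0118 | −0.0057 | 0.0005 |
| 6% vs 6% | 0 | 0 | 0 | 0 |

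Hand check on the raw scale, 8% vs 4%, survivor mean about 5: 0.04 × 2.5/4 × (24 − 5) = 0.475, close to the simulated 0.466.

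To compare with the 1-point target in section 6: one raw point, averaged over the survivor scores, is worth 0.247 (shift up) to 0.286 (shift down) asinh units. The range below pairs the smallest loss with the largest slope, and the largest loss with the smallest slope.

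- 8% vs 4%: (0.0428 − 0.0237)/0.286 = 6.7% to (0.0428 + 0.0011)/0.247 = 17.8%.
- 6% vs 4%: 0.0096/0.286 = 3.4% to 0.0219/0.247 = 8.9%.
- 10% vs 5%: 0.0234/0.286 = 8.2% to 0.0548/0.247 = 22.2%.

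**5. Imputation path.** In one simulated arm with 8% dead, a linear model for d4 on the other days predicts 5.97 for a patient with 6 on every other day if all 24s are kept, and 5.26 if all are lost. For a patient with 12 on every other day the figures are 11.74 and 9.91.

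**The case against.** The strongest reply is that the practical effect is conditional. The death statement needs a row with a follow-up date, and the listing creates no rows. The step that creates rows after death may also fill the lab fields, and other section 9 rules (discharge, carry-forward) are absent from the listing too, so unprinted code may protect the 24s. This stands: the number of affected records is unknown. It also means that if no dated row exists after death, the 24 is lost for that reason and reordering alone will not restore it.

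Second, section 9 itself sets SOFA to missing when a required lab was not ordered. That covers only the forgotten-lab statement, and it claims no priority over death. It is hard to read as applying after death, so a genuine overlap is realistic only on the day of death. The other two statements have no counterpart in section 9.

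Third, section 6 counts mortality within its missing-value percentages. That is a sample-size assumption; the same section states the death rule.

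Fourth, the percentages are not a range for this trial. This stands. The simulation has no missing scores after discharge. Adding score-dependent discharge moved the asinh loss from 0.019-0.044 to 0.025-0.055 (36% of control-arm d5 scores missing) or 0.034-0.072 (57%). The upper end of each range also requires every death-day 24 to be lost.

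**Conclusion.** The concern holds. The printed program contradicts the SAP's own death rule: a deceased patient's 24 is overwritten whenever the lab field is empty, the lab is coded as forgotten, or no lab and no reason are recorded. This follows from statement order alone and needs no assumption.

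The size does depend on assumptions. In the scenarios with unequal mortality, the loss runs from about 3% to 22% of the target difference, and 7% to 18% for 8% versus 4%. It is about zero with equal mortality, and there is no loss if the lab fields preserve every 24. The point should be fixed because it touches the primary endpoint and costs almost nothing to correct; it does not show that the trial's result is biased.

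**What to change.** 1. In Addendum 1, move the death statement after the three statements that set SOFA to missing, or restrict those three to days before death.
2. Add one sentence to section 9 saying that the death rule takes priority over the missing-lab rules.
3. Confirm that a dated record exists for every day from death to d5.
4. Check that the number of 24s assigned by the death rule equals the number of dead patient-days over d2-d5, and report both in the frequency tables that section 9 already promises. Those tables reveal a shortfall only if this comparison is made. If the analysis has already been run, the same count shows whether any 24 was lost.

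The cost is one moved SAS statement, one sentence, and a check of records and counts. No new data are needed, the written death rule does not change, and living patients' scores stay the same.
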